In this single-blinded clinical trial, the numbers of arms were randomly assigned to six groups. The participants of the study were informed about the trial but were unaware of which treatment group they were allocated to. The clinician and researcher were aware of the groups and treatments given. All patients were allocated using Block randomization. It works by dividing participants into individual blocks and then randomly assigning treatments within each block, ensuring roughly equal numbers in each group within that block. In this clinical trial, a block size of 6 (1, 2, 3, 4, 5, 6) was employed for equal enrolment. The prepared blocks were printed in sheets and patients who met the eligibility criteria were systematically assigned in a continuous fashion. After every 6th patient, the enrolment would continue on to the next block from 1.

Arms (n=84 in each)

Arm 1: Total Etch Control group (No desensitizer application)

Arm 2: Total Etch Gluma prior to acid etchant usage

Arm 3: Total Etch Gluma desensitizer application after acid etchant usage

Arm 4: Self Etch Control group (No desensitizer application)

Arm 5: Self Etch Gluma desensitizer application prior to etching

Arm 6: Self Etch Gluma desensitizer application after self-etch adhesive usage

Materials and Methodology

Caries excavation was done using diamond burs (Mani Co., Tochigi, Japan) with water coolant. Cavity extent was until sound hard or firm discolored or non-discolored dentin was achieved. This was cross-checked by an Experienced Post Graduate Supervisor (EPGS) blinded to treatment allocation group. Those teeth with width of the cavity preparation were no more than 1/3rd of the inter-cuspal width were included. Radiographs (Durr PSP Sensor, Durr, Germany) are taken to assess the depth of the

preparation and Remaining Dentin Thickness (RDT). Two RDT measurements from mesial and distal pulp horn to floor of the preparation were calculated. Mean RDT was derived from the two readings. Radiograph assessment was done by EPGS. Teeth were excluded from the study if they had pulp exposure or a prepared cavity that did not meet standardization requirements.

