In order to inhibit the enzymatic activity and increase the longevity of the bond, several materials have been investigated during the last 15 years (i.e. proanthocyanidin, genipin, tannic acid, chitosan, carbodiimide, glutaraldehyde, and chlorhexidine

GLUMA desensitizer, a solution containing glutaraldehyde (GA) and hydroxyethyl methacrylate (HEMA), is widely used to reduce sensitivity by occluding dentinal tubules and stabilizing collagen fibrils (Schupbach *et al.*, 1997)⁶. However, the ideal timing of GLUMA application in different adhesive protocols remains uncertain, raising questions about its effect on postoperative sensitivity, adhesive bond strength, and long-term restoration success.

Few studies Sayed ME *et al* 2022⁷ found that application of desensitizing agents on the prepared tooth surface for Class I cavity preparation for composite restoration reduces post- operative sensitivity where Gluma desensitizer found to reduce post-operative sensitivity when they were subjected to various stimuli such as cold drinks, intake of hot drinks, and intake of sugar for different periods of time which was scored based on the VAS (Visual Analog Scale). However the research done by Sancakli HS *et al* 2014⁸ found that no statistical differences were found with regard to post- operative sensitivity for occlusal composite restorations using different adhesive systems.

This clinical trial aims to evaluate the effectiveness of GLUMA in controlling the immediate post treatment sensitivity following occlusal composite restorations. In addition, to compare the difference between the

bonding systems (Etch-and-rinse & Self-etch) on reduction of post restoration sensitivity with or without Gluma desensitizer.

Primary Research question: Does application of Gluma desensitizer effectively reduces post-operative sensitivity following occlusal composite restoration?

For this clinical trial, a sample size of 504 restorations was calculated to be sufficient for detecting statistical difference using G* power software (α probability error – 0.05 and effect size – 0.2).

The intervention of this clinical trial is application of GLUMA Desensitizer (Heraeus Kulzer GmbH, Wehreim, Germany) which is currently available in the market as a aqueous solution containing Purified water, 35% hydroxyethyl methacrylate (HEMA), 5% glutaraldehyde, and pyrogenic silicic.

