The Kruskal-Wallis test is a non-parametric statistical test used to determine if there's a significant difference between the medians of three or more independent groups. It's an alternative to the one-way ANOVA when the data doesn't meet the assumptions of normality or equal variances.

STATISTICAL ANALYSIS OVERVIEW:

This present study contains six arms whose descriptions have been provided in the brief summary. The statistical analysis was performed using IBM SPSS version 23. The normality was assessed using Shapiro – wilks test and Q -Q plots. Since the groups do not follow the normal distribution Kruskal – Wallis test to test the statistical significance of post operative sensitivity among the groups. Mann – whitney U test was used to assess the post operative sensitivity among the control groups.

GROUPS INVOLVED:

CONTROL GROUPS:

GROUP 1: Total Etch (TE) Control Group

GROUP 2: Self Etch (SE) Control Group

TEST GROUPS:

GROUP 2: TE - GLUMA Application After Acid Etching

GROUP 3: TE - GLUMA Application Prior to Acid Etching

GROUP 5: SE - GLUMA Application Prior to Acid Etching

GROUP 6: SE - GLUMA Application After Acid Etching

NULL HYPOTHESIS:

The null hypothesis states that there is no statistically significant difference in post operative sensitivity on GLUMA application etching before or after total etching or self-etching followed by composite restoration of the carious teeth.

SAMPLE SIZE CALCULATION:

For this clinical trial, a sample size of 504 restorations was calculated to be sufficient for detecting statistical difference using G* power software (α probability error – 0.05 and effect size – 0.2).

TYPE OF ANALYSIS:

The type of trial is a Noninferiority trials. By definition a non – inferiority trial tests whether a new experimental treatment is not unacceptably less efficacious than an active control treatment already in use. With continuous improvements in health technologies, standard care, and clinical outcomes, the incremental benefits of newly developed treatments may be only marginal over existing treatments. (Hahn S. Understanding noninferiority trials. Korean journal of pediatrics. 2012 Nov 23;55(11):403.)

This test is a non - inferiority trial hence the six groups have GLUMA application before etching of a composite restoration which is not unacceptably less efficacious in reducing post operative sensitivity in composite restoration of a carious tooth.

PROCEDURE:

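### The null hypothesis concerns Gluma before versus after etching, but no before-versus-after contrast within either adhesive is specified, tested or estimated

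*Combined protocol and SAP*

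**What the plan says.** - **Hypothesis.** The SAP, under Null Hypothesis, states that "there is no statistically significant difference in post operative sensitivity on GLUMA application etching before or after total etching or self-etching".
- **Motivation.** The Background of the Brief Summary and the Introduction of the Detailed Description both say that "the ideal timing of GLUMA application in different adhesive protocols remains uncertain".
- **Primary research question** (Detailed Description). This is about Gluma against no Gluma: "Does application of Gluma desensitizer effectively reduces post-operative sensitivity following occlusal composite restoration".
- **Arms.** Arms 2 and 3 differ only in whether Gluma comes before or after the acid etchant. Arms 5 and 6 differ only in whether it comes before or after the self-etch adhesive.
- **Tests.** The Statistical Analysis Overview names a "Kruskal – Wallis test to test the statistical significance of post operative sensitivity among the groups". Of the Mann-Whitney test it says "whitney U test was used to assess the post operative sensitivity among the control groups". The Procedure section and the second Ranks table confirm that this is total-etch control against self-etch control.
- **Estimate.** The one between-arm difference given is 0.18 VAS units at 1 week, self-etch prior against total-etch after, with a one-sided 95% lower limit of +0.003.
- **Interpretation.** The Procedure section singles out self-etch with Gluma prior as lowest at every time and takes this to suggest less sensitivity.

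**The concern.** A stated hypothesis should have an analysis that can answer it. Here each reported analysis misses the timing question for a different reason. The omnibus test mixes timing, adhesive and two arms without Gluma. The pairwise test involves no Gluma at all. The estimate compares arms that differ in two factors. At stake is whether a reader can say anything about timing in either adhesive, and whether singling out one arm is backed by a comparison with the arm that differs from it only in timing.

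**Working it through.** **1. The plan's own figures reproduce, but neither concerns timing.**

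- Sample size: the plan says "a sample size of 504 restorations was calculated to be sufficient for detecting statistical difference", with "α probability error – 0.05 and effect size – 0.2". Power and the effect-size index are not stated. Reading 0.2 as Cohen's f for a six-group one-way ANOVA, N = 330, 366, 420 and 504 for power of 80%, 85%, 90% and 95%. So 504 (84 per arm) is reproduced under an assumed 95% power, for the omnibus test only.
- Estimate: 0.26 - 0.08 = 0.18. Its standard error is sqrt((0.95² + 0.27²)/84) = 0.108 (printed as 0.1077), and 0.18 - 1.645 × 0.1077 = +0.003.

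**2. The 0.18 cannot be split into adhesive and timing** (1-week means).

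- Through total-etch prior: timing 0.26 - 0.23 = 0.03, then adhesive 0.23 - 0.08 = 0.15.
- Through self-etch after: adhesive 0.26 - 0.21 = 0.05, then timing 0.21 - 0.08 = 0.13.

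The timing share is 0.03 or 0.13, depending on the route.

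**3. The missing contrasts, from the printed means, SDs and Ns.** Values are prior minus after. SE = sqrt(SD₁²/n₁ + SD₂²/n₂), with Welch 95% limits. Arm sizes are 94 and 86 (total-etch), 80 and 76 (self-etch).

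| Time | Total-etch | Self-etch |
|---|---|---|
| Pre-op | 1.72 - 1.16 = +0.56 (-0.06 to 1.18) | 0.63 - 2.11 = -1.48 (-2.07 to -0.89) |
| 24 h | 0.49 - 0.28 = +0.21 (-0.13 to 0.55) | 0.20 - 0.61 = -0.41 (-0.73 to -0.09) |
| 48 h | 0.40 - 0.28 = +0.12 (-0.18 to 0.42) | 0.03 - 0.37 = -0.34 (-0.56 to -0.12) |
| 1 week | 0.23 - 0.26 = -0.03 (-0.29 to 0.23) | 0.08 - 0.21 = -0.13 (-0.26 to 0.00) |

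The directions differ between adhesives at 24 h and 48 h and agree at 1 week. They also differ, by more, before treatment.

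**4. Record count.** The mean ranks, weighted by the printed Ns, average 126.5 at every time. Ranks of N records average (N + 1)/2, so 126.5 means N = 252; 504 records would give 252.5. With halved Ns each SE grows by √2.

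| Time | Interaction (total-etch minus self-etch) | Printed Ns | 252 records |
|---|---|---|---|
| 24 h | 0.21 + 0.41 = 0.62 | 0.16 to 1.08 | -0.02 to 1.26 |
| 48 h | 0.12 + 0.34 = 0.46 | 0.09 to 0.83 | -0.07 to 0.99 |
| 1 week | -0.03 + 0.13 = 0.10 | -0.19 to 0.39 | -0.31 to 0.51 |

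With 252 records, every post-operative interval includes zero.

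**5. Baseline.** The pre-operative interaction is 0.56 + 1.48 = 2.04 (1.19 to 2.89 on printed Ns). In change from baseline the signs reverse: total-etch 0.21 - 0.56 = -0.35, 0.12 - 0.56 = -0.44, -0.03 - 0.56 = -0.59; self-etch -0.41 + 1.48 = +1.07, -0.34 + 1.48 = +1.14, -0.13 + 1.48 = +1.35. The apparent direction depends on how baseline is handled.

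**6. Sparse scores at 48 h.** Take 252 records and integer scores, with 0 for no sensitivity. The scores that match the printed means, SDs and mean ranks give non-zero counts of 6/47 v 4/43 (total-etch) and 1/40 v 5/38 (self-etch). Mann-Whitney tests on the scores give p = 0.59 and 0.07. Fisher tests on the counts give p = 0.74 and 0.10.

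**7. The 1-week tables conflict.** On the same basis, 0.08 ± 0.27 in 40 records requires three scores of 1. The printed 1-week means and SDs allow at most 4 + 6 + 6 + 5 + 3 + 6 = 30 non-zero scores across the six arms (in table order), so at least 222 zeros, each with mid-rank of at least 111.5. The self-etch prior mean rank would then be at least (37 × 111.5 + 3 × 223)/40 = 119.9. The table prints 115.00, which fits only if all 40 scores are zero.

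**The case against.** **The null can be read globally.** Its wording is loose. Read as no difference among any of the arms, the Kruskal-Wallis test addresses it. A reader might infer that the trial cannot test its null at all; the documents do not support that. What stands is that rejecting a global null says nothing about timing. The documents also disagree on the result: the Procedure section calls 1 week significant (p = 0.013), while the note under the six-arm table calls all values non-significant.

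**Timing is not the primary question.** That question is Gluma against none, and Arms 2, 3, 5 and 6 serve it too. This limits the severity, but the SAP still writes timing into its hypothesis.

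**Pairwise tests may have been intended.** The Statistical Analysis paragraph of the Brief Summary gives the Mann-Whitney test for differences among the groups generally. It names no pairs, and the SAP names and reports only the two controls.

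**Opposite timing effects.** A reader might infer that Gluma prior helps with self-etch and harms with total-etch. The mean ranks do point opposite ways at all three post-operative times (total-etch +5.32, +4.50, +6.58; self-etch -7.32, -13.82, -19.53). The inference still fails: the 1-week means agree in direction, the pattern precedes treatment, the intervals on 252 records include zero, and the 1-week rank of one arm contradicts its mean. In addition, the SAP's group list labels total-etch Groups 2 and 3 the opposite way from the arm list. If that reached the coding, the total-etch direction flips.

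**A general message to apply Gluma first.** The text makes no such claim; it singles out the self-etch prior arm only.

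**Conclusion.** The concern holds as a gap in the analysis: the timing comparison in the null hypothesis has no matching within-adhesive contrast, and the one between-arm estimate cannot supply it. The suggestion of reduced sensitivity with self-etch prior is therefore unsupported by a timing comparison. It should be corrected, but it does not undermine the primary question.

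The size of any timing effect is unknown. Unadjusted differences run from -0.41 to +0.21 VAS units, against baseline differences of -1.48 and +0.56. No timing-by-adhesive effect is established in either direction.

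The gap itself rests on the text alone. The intervals rest on the printed means and SDs and on whether there are 504 or 252 records. The reconstructed counts assume integer scores with 0 for no sensitivity.

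**What to change.** Reconcile three things first:

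- the SAP's labels for total-etch Groups 2 and 3 with the arm list, and the coding in the data;
- the record count, 504 or 252;
- the 1-week mean (0.08) and mean rank (115.00) of the self-etch prior arm, against source records.

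Then add Arm 2 v Arm 3, Arm 5 v Arm 6 and the timing-by-adhesive interaction. Adjust for pre-operative VAS, use one row per record, and report 95% intervals with multiplicity control. Use a rank-based or penalised ordinal method: at 48 h the four Gluma arms hold 6 + 4 + 1 + 5 = 16 non-zero scores on the reconstruction, one of them in Arm 5, and an ordinary proportional-odds interaction model would be fragile.

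Label these contrasts post hoc and exploratory, since results are already printed. Do not describe Gluma prior as better, within self-etch or overall, unless they are reported.

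The cost is two more pairwise comparisons and an interaction on existing data, with wide intervals. At 84 per arm and two-sided 0.05, 80% power needs a standardised difference of about (1.96 + 0.84) × sqrt(2/84) = 0.43. With 42 per arm it needs about 0.61.

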5% of Glutaraldehyde component acts as a biological fixative, essentially coagulating proteins within the dentinal tubules and causing them to become blocked. This prevents the movement of fluid within the tubules, which is a primary cause of dentin hypersensitivity. 35% of HEMA is a hydrophilic monomer that also contributes to the occlusion of dentinal tubules. It enhances the penetration of the solution into the tubules and helps to further block the fluid flow. The mechanism of Gluma desensitizer is both the glutaraldehyde and HEMA work together to reduce the permeability of the dentin, thus minimizing the stimuli that trigger sensitivity.

In this clinical trial the numbers of arms were randomly assigned to six groups. Blinding helps to ensure that the results of the study are more reliable and less influenced by the subjective opinions or expectations of the participants or researchers. Hence in this clinical trial, single-blinding was done. The participants of the study were informed about the trial but were unaware of which treatment group they were allocated to. The clinician and researcher were aware of the groups and treatments given. This blinding was also done to minimize bias that could arise from the patient's expectations or perceptions about the treatment. In this clinical trial all the patients were allocated using Block randomization, a technique which is used to ensure balance in treatment group sizes throughout the trial. It works by dividing participants into individual blocks

and then randomly assigning treatments within each block, ensuring roughly equal numbers in each group within that block¹⁰. In this clinical trial, a block size of 6 (1, 2, 3, 4, 5, 6) was employed for equal enrolment. The prepared blocks were printed in sheets and patients who met the eligibility criteria were systematically assigned in a continuous fashion. After every 6th patient, the enrolment would continue on to the next block from 1.

Arm Title

Arm 1: Total Etch Control group (No desensitizer application) (n=84)

Arm 2: Total Etch Gluma prior to acid etchant usage (n=84)

Arm 3: Total Etch Gluma desensitizer application after acid etchant usage (n=84)

Arm 4: Self Etch Control group (No desensitizer application) (n=84)

Arm 5: Self Etch Gluma desensitizer application prior to etching (n=84)

Arm 6: Self Etch Gluma desensitizer application after self-etch adhesive usage (n=84)

Arm information and description:

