All statistical analyses were performed using non-parametric tests due to the non-normal distribution of the data, as confirmed by both the **Kolmogorov–Smirnov** and **Shapiro–Wilk** tests

($p < 0.001$). Descriptive statistics including mean and standard deviation (Mean \pm SD) were calculated for each of the six desensitizer groups at different time points: Pre-operative, 24 hours, 48 hours, and 1 week post-operative sensitivity, measured using the Visual Analog Scale (VAS).

For intergroup comparisons across all six desensitizer protocols, the **Kruskal–Wallis test** was used independently for each time point. This non-parametric method was selected to assess statistically significant differences in median VAS ranks among the groups, given the violation of normality assumptions. A separate p -value was generated for each time point:

- Pre-operative VAS: $p = 0.003$ (significant)
- 24-hour VAS: $p = 0.126$ (not significant)
- 48-hour VAS: $p = 0.050$ (borderline)
- 1-week VAS: $p = 0.013$ (significant)

Pairwise comparisons between the **Total-etch control** and **Self-etch control** groups were performed using the **Mann–Whitney U test**. This analysis revealed a statistically significant difference in pre-operative VAS scores ($p = 0.012$), while post-operative scores showed no significant differences at 24 hours ($p = 0.337$).

Mean pain scores (VAS) were also summarized for each group at all four-time intervals. The **self-etch Gluma prior to etching group consistently showed the lowest VAS scores** at all time points, suggesting reduced post-operative sensitivity in this group.

Given the minimal differences in outcome scores among the other groups, and the slightly better performance of the self-etch GLUMA prior to etching group, the data suggest that **most treatment protocols were non-inferior** to the best-performing group. Therefore, the trial was interpreted as

a **non-inferiority study**, evaluating whether the other etching and desensitizing protocols were not clinically worse than the most effective group.

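### The non-inferiority rationale misdescribes the arms and leaves two no-desensitizer controls in the comparison set, so the claim does not answer the primary question

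*Combined protocol and SAP*

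**What the plan says.** The SAP, under Type of Analysis, calls the trial non-inferiority and gives this reason: "This test is a non - inferiority trial hence the six groups have GLUMA application before etching of a composite restoration". The same section defines such a trial as testing whether a treatment is "not unacceptably less efficacious than an active control treatment already in use".

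The protocol's Arm Title list includes "Arm 1: Total Etch Control group (No desensitizer application) (n=84" and "Arm 4: Self Etch Control group (No desensitizer application) (n=84". The SAP's Groups Involved section also lists a total-etch and a self-etch control. The Detailed Description states the primary research question as "Does application of Gluma desensitizer effectively reduces post-operative sensitivity following occlusal composite restoration".

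The SAP's Procedure section refers to all six arms as desensitizer protocols. It takes self-etch Gluma prior to etching as the reference because it scored best, and describes the study as "evaluating whether the other etching and desensitizing protocols were not clinically worse than the most effective group". It concludes that the majority of protocols are non-inferior to that arm. It gives no margin, names no passing arms, and does not say which time point it means.

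**The concern.** The stated reason for the design contradicts the arm list. The definition quoted beside it does not fit a trial whose controls receive no desensitizer. The primary question asks whether Gluma does better than no Gluma, which is a superiority question.

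With all six arms counted, the five comparators are three Gluma arms and two untreated ones. A non-inferiority margin is meant to preserve part of the active treatment's effect over no treatment. If untreated arms can pass, a pass says nothing about whether that effect exists. The Procedure section nevertheless sets the claim beside a statement that sensitivity was reduced, as if one supported the other. Supplying a margin would not by itself repair this. The only pairwise test reported is control against control, so no analysis in the SAP compares a Gluma arm with its own untreated control.

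**Working it through.** **Arm structure, from the protocol's arm descriptions**

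| Arm | Adhesive | Gluma |
|---|---|---|
| 1 | Total etch | None |
| 2 | Total etch | Before |
| 3 | Total etch | After |
| 4 | Self etch | None |
| 5 | Self etch | Before |
| 6 | Self etch | After |

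Two arms of six match the SAP's rationale.

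**The plan's own figures**

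- *Sample size.* The SAP says "a sample size of 504 restorations was calculated to be sufficient for detecting statistical difference using G* power software", with "α probability error – 0.05 and effect size – 0.2". I read 0.2 as Cohen's f in a six-group one-way ANOVA (the type is not stated). The noncentral F distribution then gives N = 330, 366, 420 and 504 for power 0.80, 0.85, 0.90 and 0.95. So 504 reproduces at an assumed 95% power. It is a calculation for detecting a difference and contains no margin.
- *One-week estimate.* For total-etch Gluma after against self-etch Gluma prior, √(0.27²/84 + 0.95²/84) = 0.1078 (the SAP prints 0.1077), and 0.18 − 1.645 × 0.1077 = 0.003, as printed. Higher scores are worse, so non-inferiority turns on the other limit: 0.18 + 1.645 × 0.1077 = 0.357.

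**Margin each arm would need**

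Inputs are the means and SDs in the SAP's table and the arm sizes in its Ranks table, in arm order 86, 94, 86, 82, 80, 76. For each arm against self-etch Gluma prior:

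d = mean(arm) − mean(reference); SE = √(s₁²/n₁ + s₂²/n₂); margin needed = d + 1.645 × SE.

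Example, total-etch control at 1 week: d = 0.21 − 0.08 = 0.13; SE = √(0.77²/86 + 0.27²/80) = 0.0883; margin needed = 0.13 + 1.645 × 0.0883 = 0.275.

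| Arm | 24 h | 48 h | 1 week |
|---|---|---|---|
| Total-etch control (no Gluma) | 0.375 | 0.529 | 0.275 |
| Self-etch control (no Gluma) | 0.714 | 0.564 | 0.118 |
| Total-etch Gluma prior | 0.531 | 0.562 | 0.296 |
| Total-etch Gluma after | 0.265 | 0.418 | 0.356 |
| Self-etch Gluma after | 0.671 | 0.525 | 0.242 |
| **Smallest margin passing 3 of 5** | **0.531** | **0.529** | **0.275** |

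The total-etch control is among the first three arms to pass at every time point. At 1 week both controls are, ahead of both total-etch Gluma arms. At 24 h and 48 h the self-etch control passes last.

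**Comparison with the observed Gluma effect**

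Gluma minus its own control, with 95% CI (difference ± 1.96 × SE); negative favours Gluma:

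| Arm | 24 h | 48 h | 1 week |
|---|---|---|---|
| Total-etch prior | +0.12 (−0.23 to 0.47) | +0.03 (−0.29 to 0.35) | +0.02 (−0.21 to 0.25) |
| Total-etch after | −0.09 (−0.39 to 0.21) | −0.09 (−0.39 to 0.21) | +0.05 (−0.21 to 0.31) |
| Self-etch prior | −0.46 (−0.76 to −0.16) | −0.38 (−0.60 to −0.16) | −0.04 (−0.13 to 0.05) |
| Self-etch after | −0.05 (−0.46 to 0.36) | −0.04 (−0.35 to 0.27) | +0.09 (−0.05 to 0.23) |

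The margins needed for a majority exceed the reference arm's whole observed advantage over its own control: 0.531 against 0.46, 0.529 against 0.38, and 0.275 against 0.04.

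**Sensitivity**

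The printed mean ranks average 126.5, which fits 2 × 126.5 − 1 = 252 observations rather than 504. With arm sizes halved, the majority margins become 0.631, 0.607 and 0.336. The total-etch control still passes at each (0.459, 0.607, 0.336), and both controls pass at 1 week (0.336 and 0.150). With 1.96 in place of 1.645 and full sizes, the total-etch control needs 0.414, 0.565 and 0.303 and is again among the first three. One order does change: at 48 h with halved sizes the self-etch control (0.640) passes just before total-etch Gluma prior (0.642).

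**The case against.** The strongest reply is that the arms are described correctly elsewhere, that the SAP itself separates control from test groups, and that the Procedure section never says an untreated arm passed. All of this is true. That untreated arms must pass is an inference from the posted figures. It does not follow from counting, because three of the five comparators are Gluma arms.

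One could also read the non-inferiority set as the three other Gluma arms, so that a majority is two of three. At 48 h a margin between 0.525 and 0.529 would then pass two Gluma arms and no control. The Procedure section's count of six protocols does not support that reading. Even on it, a majority needs 0.531 at 24 h and 0.296 at 1 week, which again pass one control and both controls respectively.

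Three stronger readings are tempting and should be resisted.

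- *That the claim amounts to a negative answer on Gluma.* It does not. Non-inferiority of an untreated arm can coexist with superiority of the reference: at 48 h the self-etch control would pass at 0.57, yet its difference from the reference excludes zero in Gluma's favour.
- *That the framework cannot tell an effective desensitizer from none.* Margins from 0.531 up to 0.714 at 24 h, and from 0.529 up to 0.564 at 48 h, pass a majority while the self-etch control, the like-for-like comparator, fails. The total-etch control's comparison with a self-etch arm mixes adhesive with Gluma.
- *That the untreated arms were not separated from the best Gluma arm.* On the same approximation both controls are separated at 48 h (total-etch +0.34, 95% CI 0.12 to 0.56; self-etch +0.38, 0.16 to 0.60), and the self-etch control at 24 h (+0.46, 0.16 to 0.76). The statement holds only for the total-etch control at 24 h and for both controls at 1 week.

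**Conclusion.** The point stands and needs correcting before the conclusion is relied on. The rationale is wrong for four of six arms, the definition does not fit untreated controls, and the claim does not answer the primary question. These conclusions need no calculation.

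The size rests on the posted summaries. Any margin that makes a majority of the five comparators non-inferior also passes the total-etch control at all three times and both controls at 1 week, and it is larger than the reference arm's observed advantage over its own control.

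The limits are normal approximations on skewed scores, and the number of observations is in doubt. The raw differences do not isolate Gluma either: the groups differ before treatment (Kruskal–Wallis p = 0.003), and the reference arm has the lowest pre-operative mean (0.63, against 1.88 in its own control). The self-etch differences at 24 h and 48 h therefore justify a proper superiority analysis but do not replace one.

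**What to change.** In Type of Analysis, replace the rationale with the true arm structure and name Arms 1 and 4 as no-treatment controls. Make the Gluma question a superiority contrast of Gluma against no Gluma within each adhesive. Remove Arms 1 and 4 from any non-inferiority set. Limit any such claim to comparisons among Gluma arms, with a justified margin, and read it only if the reference arm is first shown superior to its own control.

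In Procedure, delete the sentence that most protocols were non-inferior. Do not replace it with a statement that the untreated arms were not separated from the best Gluma arm. Report the Gluma-minus-control differences with intervals at 24 h, 48 h and 1 week, and state that non-inferiority does not show that Gluma reduces sensitivity.

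The cost is SAP wording, a within-adhesive analysis of existing data and a restated conclusion; no new data are needed. The downside is that the stated conclusion becomes less favourable.
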